6.1 General Statistical Methodology

Descriptive summaries will be provided where appropriate for each of the primary and secondary variables. In general, tables will summarize data by treatment groups.

In general, baseline and safety tables will be completed for the safety population unless otherwise specified. Efficacy tables will be presented for the ITT population and will be also completed for the PP population.

PK/PD tables will be produced for the PK/PD population, and the PK/PD profile subset.

The Analysis populations will be used according to [Table 1](#).

Table 1: Analyses populations

Analyses	Safety Analysis Population	ITT Population	Per Protocol Population	PK/PD Population/ Profile Subset
Baseline Assessments (including inclusion/exclusion criteria and eligibility, prior therapies)	X	X	X	
Compliance and Exposure	X			
Safety (including concomitant therapies)	X			
Pharmacokinetics/ Pharmacodynamics				X
Efficacy		X	X	

Continuous, quantitative (absolute values at each timepoint and change from baseline if applicable) variable summaries will include the number of subjects (N) with non-missing values, mean, standard deviation (SD), standard error (SE) of the mean, median, minimum, and maximum, unless otherwise specified.

Categorical, qualitative, variable summaries will include the frequency and percentage of subjects who are in the particular category. In general the denominator for the percentage calculation will be based upon the total number of subjects in the study population for the cohorts, unless otherwise specified. Where appropriate, the presentation of results will include shift tables, plots or confidence intervals.

All analysis will be performed using SAS® Software version 9.4 or later.

All PK/PD parameter estimations will be performed using Phoenix WinNonlin® version 6.4 or later.

6.1.1 Baseline Data

Baseline is defined as data collected at Visit 1. If data are missing at Visit 1, then data from screening will be used as baseline instead.

6.1.2 Handling of Missing Data

Missing height velocity will be imputed by a multiple imputation method as the primary analysis for subjects who prematurely discontinued for the primary endpoint:

Subjects with missing primary endpoint will have height value imputed using a multiple imputation model that contains the following variables: gender, baseline age, peak GH levels (log-transformed) at stimulation test, baseline height SDS – average SDS of parental height, and height values at post-baseline visits. The multiple imputation will be stratified by treatment ([4-5]), which is detailed in [Section 8.1](#).

Imputation of missing data will be conducted under a working assumption of missing at random (MAR). Missing at random means that the missing data mechanism is assumed not to depend on unobserved missing values but may depend on any other available information collected in the trial.

The imputations will be performed for post-baseline visits. The Markov Chain Monte Carlo (MCMC) method will be used under the multivariate normality assumption to impute the missing height values by treatment group. The variable list for imputations will include gender, baseline age, peak GH levels (log-transformed) at stimulation test, baseline height SDS – average SDS of parental height, as well as all available post-baseline height values. The SAS procedure PROC MI will be used in the multiple simulation. The MCMC method will impute 100 datasets. Multiple imputation replaces each missing value with a set of $m = 100$ plausible possibilities. The set of these possibilities represent the uncertainty about the unobserved ‘true’ value that was imputed.

6.1.2.1 Step I: Imputation of Missing Data

Default EM algorithm will be used to derive a set of initial parameter estimates for MCMC method. A non-informative prior (default Jeffreys’ prior) will be used to derive the posterior distribution of the parameters. Trace plots and autocorrelation plots of the variables will be examined. The number of burn-in iterations may be modified (the default is 200 burn-in iterations) to ensure the iterations converge to the stationary distribution before the imputation.

The following pseudo SAS code and seed (301) will be used:

```
*****  
* Note: *  
* AAGE = Baseline age *  
* PEAKGHLG = Peak GH levels (log-transformed) at stimulation test *  
* TRT01P = Treatment group: Genotropin, TransCon hGH *  
* DMPHTSDS = Baseline height SDS – average SDS of parental height *  
* SEXN = Gender: 1 – Male; 0 - Female *  
*****  
proc sort data=indsn;  
  by TRT01P SUBJID;  
run;  
  
proc mi data=indsn seed = 301 nimpute = 100 out=imputed;  
  mcmc chain=single initial=em (maxiter=1000) niter=1000 nbiter=1000;  
  by TRT01P;  
  var AAGE PEAKGHLG DMPHTSDS SEXN week5 week13 week26 week39 week52;  
run;
```

6.1.2.2 Step II: Inference

For each of the 100 imputed datasets, height velocity will be recalculated based on the multiply imputed height values. The primary efficacy analysis will then compare the annualized height velocity at Week 52 between TransCon hGH and Genotropin groups in the ITT population. The data will be analyzed using an analysis of covariance (ANCOVA) model with treatment and gender as factors, baseline age, baseline peak GH levels (log transformed) at stimulation test, and baseline height SDS - average SDS of parental height as covariates.

The sample SAS code for the ANCOVA model can be found below:

```
*****
* Note:                                                                 *
*   AAGE = Baseline age                                               *
*   PEAKGHLG = Peak GH levels (log-transformed) at stimulation test   *
*   DMPHTSDS = Baseline height SDS – average SDS of parental height  *
*   _IMPUTATION_ = Iteration number in the multiple imputation       *
*   TRT01P = Treatment group: Genotropin, TransCon hGH              *
*   SEX = Gender                                                       *
*****

ods output lsmeans=lsm diffs=diff;
proc mixed data = ADEFF;
  by _imputation_;
  class TRT01P(ref='Genotropin') AVISIT SEX;
  model AVAL= AAGE PEAKGHLG DMPHTSDS TRT01P SEX/solution cl;
  lsmeans TRT01P/e diff cl;
  where AVISIT='Week 52' and PARAMCD='HGHTVEL' and ANL01FL='Y' and ITTFL='Y';
run;
```

The estimates from the 100 fitted models for each of the 100 imputed datasets will be combined to provide an overall estimate of the least square mean with a corresponding confidence interval for each treatment group and an overall estimate of the difference in least square means between the two treatment groups and a p-value ([6]). The following pseudo SAS code will be used:

```
proc sort data=lsm;
  by trt01p;
run;
```

```
ods output ParameterEstimates=miest_lsm;
proc mianalyze data=lsm;
  by trt01p;
  modeleffects estimate;
  stderr stderr;
run;
```

```
ods output ParameterEstimates=miest_diff;
proc mianalyze data=diff;
  modeleffects estimate;
  stderr stderr;
run;
```

The primary analysis model with ANCOVA will be repeated in the PP population. Because the PP population excludes subjects who have missing data at Week 52, the multiple imputation method described above will not be used for the PP analysis.

For categorical variables, the worse case (non-responder) imputation will be applied to impute missing data for ITT analysis.

If growth hormone stimulation data is missing at diagnosis, for example due to structural abnormalities leading to hypopituitarism, a value of 2 ng/mL will be used by convention.

For subjects missing height data for one of the two parents, the average parental height SDS will be estimated based on the non-missing parental height SDS. For subjects with no parental height data, the population median parental height SDS from all subjects with parental height data will be imputed.

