3.2 Sample Size and Subject Population

This is a pivotal clinical trial intended to support market approval.

Based on the Phase 2 trial (Protocol ACP-001_CT-004) and similar growth hormone studies published in the literature, and assuming a SD of 3.5 cm/year with a non-inferiority margin of 2.0 cm, a sample size of 147 subjects in the ITT population will be needed to show non-inferiority of TransCon hGH treatment compared to daily hGH with a power of 90%. This sample size calculation is based on a 2:1 randomization and a 1-sided alpha level of 0.025.

A sample size of 150 subjects randomized has been chosen to account for slight imbalances in the randomization due to stratification of randomization. For 150 enrolled subjects, approximately 450 subjects may need to be screened in the trial.

Approximately 150 prepubertal, hGH-treatment naïve children (males and females) with GHD will be included. Subjects will be allocated to 1 of 2 treatment groups in a 2:1 ratio:

- Two thirds of the 150 subjects (approximately 100 subjects) will receive TransCon hGH treatment to obtain an expected 90 per protocol subjects in this cohort
- One third of the 150 subjects (approximately 50 subjects) will receive Genotropin treatment to obtain an expected 45 per protocol subjects in this cohort

4. Analysis and Reporting

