All statistical tests except non-inferiority tests will be based on a 2-sided test at the significance level of 0.05 and 95% confidence intervals, unless otherwise specified. Non-inferiority tests will be based on a one-sided significance level of 0.025.

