8.1 Primary Efficacy Variable Analysis

The absolute values and mean change from baseline at each timepoint of the annualized height velocity will be presented by treatment group with descriptive statistics.

The primary endpoint, annualized height velocity at week 52, will be compared between TransCon hGH treatment and daily hGH treatment, by a non-inferiority comparison with a non-inferiority margin of 2.0 cm/year, followed by a test of superiority if non-inferiority is established.

As the primary analysis, an ANCOVA model will be used to analyze annualized height velocity at week 52, after potential multiple imputation as described in [Section 6.1.2](#). The annualized height velocity at week 52 will be included in the model as a response variable. The model will include baseline age, peak GH levels (log transformed) at stimulation test, baseline height SDS – average SDS of parental height as covariates, treatment and gender as factors. The estimates from the 100 fitted models for each of the 100 imputed datasets will be combined to provide an overall estimate of the between treatment group difference with a corresponding confidence interval and a p-value.

For the primary efficacy analysis, a 2-sided 95% confidence interval will be calculated for the difference in least square means between the 2 treatment groups [TransCon hGH treatment minus daily hGH] at Week 52. If the lower confidence bound is >-2.0 cm, non-inferiority is demonstrated in terms of effectiveness. If the lower confidence bound is >0 , superiority is established.

Treatment-by-covariate interaction will be examined as appropriate as part of the analysis model examination.

Height velocity at other post-baseline visits will be analyzed similarly using the same ANCOVA model as described above for the primary efficacy analysis. The same ANCOVA model described above will also be used to analyze observed cases as a sensitivity analysis of the primary analysis.

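### The pooling of the 100 primary ANCOVA fits has no degrees-of-freedom rule; run as written with complete-data df taken as infinite, it makes the deciding 95% CI about 0.9% too narrow

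*SAP*

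**What the plan says.** SAP 6.1.2.2 fits an ANCOVA to each of 100 imputed datasets. The model has three covariates (age, log peak GH, and baseline height SDS minus average parental height SDS) and two factors (treatment and sex). For the pooling the section states: "The following pseudo SAS code will be used". The code has two PROC MIANALYZE calls, one for the least square means and one for the treatment difference, "proc mianalyze data=diff". Each contains only a MODELEFFECTS and a STDERR statement. Neither sets a complete-data df, and the PROC MIXED residual df are not carried forward.

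The text of 6.1.2.2 cites reference [6] for the combination. SAP 8.1 says the fits are "combined to provide an overall estimate of the between treatment group difference with a corresponding confidence interval and a p-value". Neither section writes out a df rule. SAP 8.1 makes the lower limit of the pooled two-sided 95% interval the criterion for non-inferiority (above -2.0 cm) and then superiority (above 0). The opening of SAP section 8 sets the level: "Non-inferiority tests will be based on a one-sided significance level of 0.025".

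Two related analyses are not pooled. On per-protocol, 6.1.2.2 says: "The primary analysis model with ANCOVA will be repeated in the PP population", without imputation. On observed cases, 8.1 says: "The same ANCOVA model described above will also be used to analyze observed cases as a sensitivity analysis of the primary analysis".

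**The concern.** Each single ANCOVA has a finite residual df, about 144, and its interval should use a t quantile on that df. Rubin's large-sample df formula assumes the complete-data df are infinite. With very few missing values it returns df in the hundreds of thousands or more, so the pooled interval is in effect a normal interval. The small-sample adjustment of Barnard and Rubin corrects this, but it needs the complete-data df, which the written calls do not supply.

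Two programs that both satisfy the prose can therefore give slightly different deciding intervals, and the one printed in the SAP gives the narrower. That direction favours the sponsor for both non-inferiority and superiority. The per-protocol and observed-case ANCOVAs would rest on residual df, so the primary interval would also differ from its own checks through a change of reference distribution that has nothing to do with missing data.

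**Working it through.** **Inputs from the documents.** m = 100 imputations (SAP 6.1.2). ANCOVA rank 6: intercept, age, log peak GH, height SDS minus parental SDS, treatment and sex (SAP 6.1.2.2). N = 147 required and 150 randomized, 2:1, SD 3.5 cm/year, margin 2.0 cm, one-sided 0.025, 90% power (SAP 3.2). Two early discontinuations (SAP document history, entry for 5.0).

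**Assumptions.** When no complete-data df is supplied, the software takes it as infinite. The relative increase in variance from missing data, r, is not in the documents; it is varied from 0.002 to 0.02, which covers about two missing values in 150. The true difference behind the sample size is taken as 0.

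**Plan's own figure.** Control arm n = (1 + 1/2) × [3.5 × (1.960 + 1.282)/2.0]² = 48.3, rounded up to 49; with 98 on the weekly product the total is 147. The stated size is reproduced.

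**Degrees of freedom.** Complete-data df: ν₀ = N - 6, which is 144 at N = 150 and 141 at N = 147.

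- Rubin, infinite ν₀: ν = (m - 1)(1 + 1/r)². At r = 0.01 this is 99 × 101² = 1,009,899.
- Barnard-Rubin: ν_obs = ν₀(ν₀ + 1)/(ν₀ + 3) × 1/(1 + r), then 1/ν* = 1/ν + 1/ν_obs. At N = 150 and r = 0.01, ν_obs = (144 × 145/147)/1.01 = 140.6, and ν* = 140.6.

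| N | r | Rubin df | t | Barnard-Rubin df | t | Width ratio | One-sided error |
|---|---|---|---|---|---|---|---|
| 150 | 0.002 | 24.8 million | 1.9600 | 141.8 | 1.9768 | 0.9915 | 0.0260 |
| 150 | 0.01 | 1.01 million | 1.9600 | 140.6 | 1.9770 | 0.9914 | 0.0260 |
| 150 | 0.02 | 257,000 | 1.9600 | 139.2 | 1.9772 | 0.9913 | 0.0260 |
| 147 | 0.002 | 24.8 million | 1.9600 | 138.8 | 1.9772 | 0.9913 | 0.0260 |
| 147 | 0.01 | 1.01 million | 1.9600 | 137.6 | 1.9773 | 0.9912 | 0.0260 |
| 147 | 0.02 | 257,000 | 1.9600 | 136.2 | 1.9775 | 0.9911 | 0.0260 |

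The width ratio is the first t over the second. The error is the upper tail beyond 1.960 of a t distribution on the Barnard-Rubin df.

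**Shift in the lower bound (100:50, r = 0.01).** SE = SD × √(1/100 + 1/50). The 3.5 row uses the planning SD and is an upper case if the covariates explain variance.

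| Residual SD (cm/year) | SE | Half-width, 1.960 | Half-width, 1.977 | Shift |
|---|---|---|---|---|
| 3.5 | 0.606 | 1.188 | 1.198 | 0.010 |
| 3.0 | 0.520 | 1.018 | 1.027 | 0.009 |
| 2.5 | 0.433 | 0.849 | 0.856 | 0.007 |
| 2.0 | 0.346 | 0.679 | 0.685 | 0.006 |

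**Probability of declaring non-inferiority** (noncentral t on 140.6 df, SD 3.5, N = 150), with 1.960 and with 1.977:

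- true difference -2.0: 0.0260 against 0.0250, a gap of 0.10 percentage points;
- true difference 0: 0.9088 against 0.9060, a gap of 0.28 points;
- the largest gap is 0.67 points, near a true difference of -0.8 (0.69 points at N = 147).

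**The case against.** The documents do not say what PROC MIANALYZE does when no complete-data df is given, so every figure rests on an assumption about software; if that is wrong, the numerical error vanishes. This stands as a condition on the size. It does not affect the finding that no df rule is written down.

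The code is labelled pseudo code and is visibly incomplete: the step that turns imputed heights into height velocities appears only in prose. A final program that adds EDF= would comply with the text. That is fair, and it makes this a specification gap combined with code that omits the option, not proof of what will be run. But the SAP says this code is what will be used.

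Reference [6] may contain a df rule. It cannot be checked here, and citing it does not change the df available to the written calls.

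Imputation may not occur: 8.1 itself says "after potential multiple imputation". With two early discontinuations it is a realistic prospect, but few values would be involved.

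The plan does explain why the per-protocol analysis is not pooled (it excludes subjects without Week 52 data), and observed cases leave nothing to pool. Only the change of reference distribution is unexplained. Finally, the effect is tiny, and the observed-case ANCOVA should nearly duplicate the primary result on residual df, so a borderline case would be seen. All of this stands and is why the point is minor.

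**Conclusion.** The concern holds and is minor. The SAP gives no df rule for the interval that decides the trial, and the code it prints supplies no complete-data df. The numerical consequence needs all three conditions: the code is run as written, the software takes the complete-data df as infinite, and at least one Week 52 height is imputed. The deciding interval is then about 0.9% too narrow and the one-sided error about 0.026 where the plan states 0.025, for both the non-inferiority and the superiority test. At the planning SD the bound moves by 0.010 cm/year, which is 0.5% of the 2.0 cm margin, and by less if the residual SD is smaller. A conclusion could change only for a bound within that distance of -2.0 or 0.

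**What to change.** In SAP 6.1.2.2, add EDF= to both PROC MIANALYZE calls, set to the PROC MIXED residual df (N-6, where N is the number of subjects in the fitted ANCOVA). Add one sentence stating that pooled intervals and p-values use small-sample-adjusted (Barnard-Rubin) degrees of freedom.

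The cost is one option in two calls and one sentence. No new data are needed, and the imputation model and the ANCOVA do not change. The pooled interval becomes about 0.9% wider than under the code as written, and power at the planning assumptions goes from 90.9% to 90.6% at N = 150.

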6.1.3 Visit Windows

Table 2: Bioanalytical Samples visit windows from Visits 1 to 6

Visit	Time Relative to Dosing, by Visits (Hours)					
	1	2	3	4	5	6
TransCon hGH	predose, morning	predose, morning	48-72h, morning	48-72h, morning	48-72h, morning	164-172h, morning
Week	1	5	13 (+2)	26 (±1)	39 (±1)	52 (+1)
Day	1	29	87-88	178-179	269-270	365
Genotropin	predose, 2h, morning	morning	morning	morning	morning	morning
Week	1	5	13 (+2)	26 (±1)	39 (±1)	52 (+1)
Day	1	29-35	85-91	176-182	267-273	365

Abbreviation: hGH=human Growth Hormone

TransCon hGH Cohort (Cohort 1)

- Visits 1 and 2 will be performed on the day of the 1st and 5th dosing (Days 1 and 29), respectively.
- Visits 3, 4 and 5 will be performed 48-72 hours after the 13th, 26th and 39th dose, respectively.
- Visit 6 will be performed 7 days after the last dose (Day 365).

All attempts should be made to adhere to the planned visit schedule as specified per [Table 2](#). However, in case the subject is not able to attend Visits 3, 4, 5 and 6 during Week 13, 26, 39 or 52, respectively, these visits can be performed with a + 2 week window for Visit 3, meaning either Week 14 or 15, if Week 13 is not achievable; and a ± 1 week window for Visits 4, and 5, meaning either Week 25 or 27, if Week 26 is not achievable or Week 38 or 40, if Week 39 is not achievable; and a + 1 week visit window for Visit 6, meaning Week 53, if Week 52 is not achievable.

Genotropin Cohort (Cohort 2)

- At Visit 1, subjects will be dosed in the morning at the clinic.
- All subjects in the Genotropin cohort will attend Visit 1 fasting with administration of the dose at the investigational site and predose sampling and will have an additional postdose sampling for hGH at 2 hours.
- Visits 2, 3, 4 and 5 will be performed on any day during Weeks 5, 13, 26 and 39, respectively. Preferably, all clinic visits will be in the morning for consistency of auxology measurements. Visit 4 needs to be conducted in the morning hours, since the subject is requested to be fasting. Visit 6 will be performed 1 day after the last dosing (Day 365) in the morning hours, since the subject is requested to be fasting.

All attempts should be made to adhere to the planned visit schedule as specified per [Table 2](#). However, in case the subject is not able to attend Visit 3, 4, 5 and 6 during Week 13, 26, 39, or 52, respectively, these visits can be performed with a + 2 week window for Visit 3, meaning either Week 14 or Week 15, if Week 13 is not achievable; and a ± 1 week visit window for Visits 4 and 5, meaning either Week 25 or 27, if Week 26 is not achievable or Week 38 or 40, if Week 39 is not achievable; and a + 1 week visit window for Visit 6, meaning Week 53, if Week 52 is not achievable.

Post-baseline unscheduled visit (occurred after the date of initiation of the first dose) or end of study visit (early termination visit) will be mapped to the post-baseline scheduled visit with the closest target study day for each scheduled assessment per [Table 3](#). If the unscheduled visit is in the middle of two scheduled visits, map it to the later one. After mapping, if there are more than one visits in the same window, the visit closer to the target assessment day will be used. If more than one visits have the equal distance to the target day then the later one will be used, if more than one visits on the same day, use the time or the sequence number to select the later record. For listings and shift tables, all data points will be included.

Table 3: Analysis Window to Map Unscheduled and Early Termination Visits

VISIT	Week	Target Study Day	Study Day Window
Visit 1	Week 1	1	<=1
Visit 2	Week 5	29	2-58
Visit 3	Week 13 (± 2 Week)	88	59-133
Visit 4	Week 26 (± 1 Week)	179	134-224
Visit 5	Week 39 (± 1 Week)	270	225-317
Visit 6	Week 52 (+ 1 Week)	365	>=318

6.2 Derived and Computed Variables

The following derived and computed variables have been initially identified as important for the analysis of the safety, efficacy or PK/PD as appropriate. It is expected that additional variables will be required. The SAP will not be amended for additional variables that are not related to the primary target or key secondary target variables. Any additional derived or computed variables will be identified and documented in the SAS programs that create the analysis files.

Parameter	Description of Parameter
Date of Birth	Day of 15 is used to impute the day for all birth date
Age (Years)	$(\text{Date of Measurement} - \text{Date of Birth}) / 365.25$
Age (Months)	$((\text{Date of Measurement} - \text{Date of Birth}) / 365.25) * 12$
C _{max}	The maximum serum concentration observed.
Annualized Height Velocity at visit x (HV) cm/year	$[(\text{HT}(\text{Visit } x) - \text{HT}(\text{Visit } 1))] * 365 / [(\text{Date}(\text{Visit } x) - \text{Date}(\text{Visit } 1))]$
Change from baseline over 52 weeks	The value of each variable at each post-baseline timepoint minus the baseline score. The change from baseline will be calculated for: 
 • change in height (HT) SDS • change in serum IGF-1 • change in serum IGFBP-3 • change in IGF-1 SDS • change in IGFBP-3 SDS
Normalized serum IGF-1 SDS	Proportion of subjects with IGF-1 Standard Deviation Score (SDS) of 0 to +2.0. Also derive for -2.0 to +2.0, -1.0 to +2.0.

Parameter	Description of Parameter
Total duration of treatment (day)	
TransCon hGH Last dose date – first dose date + 7
 
Genotropin Last dose date – first dose date + 1

Total number of planned doses	
TransCon hGH Round (Last dose date – first dose date + 7)/7 to the nearest integer
 
Genotropin Last dose date – first dose date + 1

Total Actual Dosage (mg)	
TransCon hGH Sum Concentration (mg/mL) x volume (mL) over all injections
 
Genotropin Sum dose (mg) over all injections

Parents' Height SDS	
$((\text{Parents Height}/M)^L - 1)/(L \times S)$
 
Where M=median , S= generalized coefficient of variation, and L= power in the Box-Cox transformation, the M, S, L values are obtained from the CDC website; Percentile Data Files with LMS Values

Region	
 • Australia and New Zealand will be mapped to 'Oceania' • Belarus, Bulgaria, France, Georgia, Germany, Greece, Italy, Poland, Romania, Russia and Ukraine will be mapped to 'Europe' • Canada and United States of America will be mapped to 'North America' • Egypt and Jordon will be mapped to 'Middle East and North Africa' • Turkey and Armenia will be mapped to 'Asia'
Height Velocity at Baseline	
Calculated based on the height measurement pre-dose, with the measurement closest to the time of one year before baseline if we have multiple height measurements before baseline. If the there are two measurements with equal distance to one year prior to baseline, we use the one closer to baseline of the two to calculate baseline height velocity

Parameter	Description of Parameter
Height SDS	Height expressed in Standard Deviation Score (SDS) is derived using CDC 2000 (United States of America)/Kuczmarski method as $((\text{Height}/M)^L - 1) / (L \times S)$. Where M=median , S= generalized coefficient of variation, and L= power in the Box-Cox transformation, the M, S, L values are obtained from the CDC website; Percentile Data Files with LMS Values. M, L, and S need to be interpolated based on the next lower age category, and the next upper age category.
Height Velocity SDS	The Height Velocity expressed in SDS is derived as follows. $\text{HV SDS} = (\text{Observed HV} - \text{Reference HV}) / \text{Reference HV SD}$. Mean age at the two visits where HV is calculated will be used to determine reference HV and HV SD. Mean HV and SD HV are defined by age categories between male and female as in the Tanner's publication [7a, 7b]. Reference HV and HV SD are interpolated based on the lower age category and the next upper age category and mean age

The following variables are automatically calculated in the eCRF. However, the reference methods for calculation are reported in the following table for completeness of information.

Parameter	Description of Parameter
Birth Weight SDS	The Birth Weight Standard Deviation Score is calculated in the eCRF using the method described in [8]

